The PK-222-L ECG cable patient cable is used with a surface ECG to connect the ECG electrodes to a programmer from BIOTRONIK. As part of implantations and follow-ups of IPGs, ICDs, CRTs and ICMs from BIOTRONIK, the signals are transmitted via the patient cable for representation of the surface ECG on the screen. The ECG cable PK-222-L differs from the approved PK-222-EU cable in its length and the permanently mounted patient cable electrode clips.

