4.3 Model name including software version and accessories

The devices undergoing clinical investigation are BIOTRONIKs Renamic Neo programmer, the programmer software NEO 2001.A and the ECG cable PK-222-L. These investigational devices have not been approved for the market release yet by a regulatory authority or notified body. Clinical data on these devices are collected to support regulatory approval.

Table 1: Investigational Devices

Model Name	Model Number
Renamic Neo	424722
including rechargeable battery	445510
Programmer software NEO 2001.A and successor	449859
PK-222-L ECG cable	429747

In addition, data on the following BIOTRONIK available accessories (additional devices) may be collected, as required to support regulatory requirements (Table 2). Except for the accessory bag the listed accessories used in the scope of this clinical study are certified by the Australian Therapeutic Goods Administration (TGA).

Table 2: Available Accessories

Model Name	Model Number
Accessory bag	445749
PK-222 EU / 2.8 m ECG cable	335284
PK Electrode Clip	340293
Patient cable PK-141	353181
Patient cable PK-67-S	128085
Patient cable PK-67-L	123672
Patient cable PK-155	337358
Patient adapter PA-1-B	123751
Patient adapter PA-1-C	349723
Patient adapter PA-2	123157

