7 OBJECTIVES AND HYPOTHESES

7.1 Objectives

This study is designed as a pre-market clinical study to provide evidence on the safety, performance and usability of the Renamic Neo programmer hardware, software and ECG cable PK-222-L to support regulatory approval, with a focus on requirements of the European Medical Device Regulation (MDR). The study is also intended to identify and evaluate residual risks associated with the use of the Renamic Neo programmer system that remained unrevealed even after risk analysis, risk mitigation and completed validation of the device. The results will be used to update the clinical evaluation of the devices.

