9 STUDY PROCEDURES

9.1 Overview

Patients will be enrolled either for implantation including subsequent pre-hospital discharge or for a follow-up visit only. ICM patients will be included for follow-ups only. As the total study duration is planned for only 3 months different patients will be included for implantation and for follow-up. Patients that have been enrolled in the study and were terminated shall not be included a second time in the study.

All study related procedures performed (Table 3) have to be documented in the CRFs.

Table 3: Overview of study procedures

Investigations	Enrollment / Baseline	For patients enrolled before implantation		For patients enrolled after implantation
		Implantation	Pre-hospital discharge	Follow-up
Patient informed consent	x			
Verification of in- and exclusion criteria	x			
Demographics and medical history	x			
Information on implanted IPG, ICD, CRT or ICM, leads (device log)	x*	x		
PSA measurements and evaluation		x		
Device based measurements and evaluation, if applicable		x	x	x
Evaluation of implant interrogation and programming functionality		x	x	x
General assessment of Renamic Neo hardware and software		x	x	x
Evaluation of usability of Renamic Neo system		x	x	x
Data export (connectivity, printing)		x	x	x
Data export of use case data for evaluation at sponsor		x	x	x
Used accessories (including entry in device log)		x	x	x
Battery usage		x	x	x
Adverse event and device deficiency reporting	x	x	x	x
Concomitant medication	x ¹	x ¹	x ¹	x ¹
Regular termination			x	x

x point in time of study procedure depends if patient is enrolled for implantation use case (includes PHD) or for follow-up use case.

x* point in time for follow-up cases

x¹ only if related to an AE

All Renamic Neo programmer systems at a given site should be used roughly for the same number of use cases. Further measures to avoid bias are described in section 8.1.2. This

includes the distribution of implantation and follow-up cases between implant types. The use of the ECG cable PK-222-L is optional but use and evaluation have to be documented in the respective CRFs.

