Data file, identifier patient display id full & SVTYP & helpvar model & DIPRGSNR	Notes	Variable name	Variable label	Variable level	Nominal values
accessory log details (see Analysis Set and Data Selection)	no report	DIECBMDL	ECG cable model	nominal	o PK-222-L ECG cable o PK-222 EU / 2.8 m ECG cable
		QSECBAS	Usage of ECG cable	nominal	o used successfully o used, but not successfully
		QSECBPRB	Did you notice any problems related to ECG cable	nominal	o Yes, with Adverse Event o Yes, without Adverse Event o No problem detected

Data file, identifier patient display id full & SVTYP & helpvar model & DIPRGSNR	Notes	Variable name	Variable label	Variable level	Nominal values
accessory log details (see Analysis Set and Data Selection)	case listing for QSECBAS = used, but not successfully OR QSECBPRB = Yes, with Adverse Event OR QSECBPRB = Yes, without Adverse Event including programmer serial number DIPRGSNR (see note before)	COECBAS	NEW: ECG cable at investigation: Please specify reason for unsuccessful use	text	...

Data file, identifier patient display id full	Notes	Variable name	Variable label	Variable Level	Nominal values
data SAR	descriptive	n ecgcable PK imp SAR 	Number of PK ECG cables used during implantation	metric to be reported as nominal	o 1 o 2 ...
		n ecgcable PK222L imp SAR 	Number of PK-222-L ECG cables used during implantation	metric to be reported as nominal	o 1 o 2 o ...
		n ecgcable PK222EU imp SAR 	Number of PK-222-EU ECG cables used during implantation	metric to be reported as nominal	o 1 o 2 ...
		n ecgcable nosuccess imp SAR 	Number of ECG cables not successfully used during implantation	metric to be reported as nominal	o 1 o 2 ...
		n ecgcable problem imp SAR 	Number of ECG cables with any problem used during implantation	metric to be reported as nominal	o 1 o 2 ...

 Count DIECBMDL = "PK-222-L ECG cable" OR "PK-222 EU / 2.8 m ECG cable" per patient display id full

 Count DIECBMDL = "PK-222-L ECG cable" per patient display id full

 Count DIECBMDL = "PK-222 EU / 2.8 m ECG cable" per patient display id full

 Count QSECBAS = "used, but not successfully" per patient display id full

 Count QSECBPRB = "Yes, with Adverse Event" OR "Yes, without Adverse Event" per patient display id full

Electrode clip

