### 16.1. Analysis Set and Data Selection

All analyses are performed for patients in the PHD and follow-up analysis set using a specific data selection after implantation.

All analyses from chapter 15 Devices and Accessories - Implantation are repeated for these data. However, "implantation" will be replaced by and "PHD & follow-up".

---

 analysis set PHD FUP SAR = Yes  
Data selection for accessory log details with SVTYP ≠ implantation

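### SAP 15.1 tabulates use of the investigational PK-222-L ECG cable by model, but pools its unsuccessful uses and problems with those of the certified PK-222 EU

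*SAP*

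**What the plan says.** Protocol 7.1 states that the study is meant "to provide evidence on the safety, performance and usability of the Renamic Neo programmer hardware, software and ECG cable PK-222-L". Protocol 4.3 lists PK-222-L as one of the investigational devices. The other ECG cable, PK-222 EU, is in that section's accessory table, of which it says: "Except for the accessory bag the listed accessories used in the scope of this clinical study are certified". Protocol 4.1 describes the design difference: "The ECG cable PK-222-L differs from the approved PK-222-EU cable in its length", and also in its permanently mounted electrode clips. Protocol 9.1 adds: "The use of the ECG cable PK-222-L is optional but use and evaluation have to be documented in the respective CRFs".

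In SAP 15.1 (ECG cable), the two models share one success variable (QSECBAS) and one problem variable (QSECBPRB). The model is held in DIECBMDL. Five counts are derived from these:

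- Footnote 37 counts uses of either model.
- Footnote 38 counts PK-222-L uses: "Count DIECBMDL = 'PK-222-L ECG cable' per patient display id full".
- Footnote 39 does the same for PK-222 EU.
- Footnote 40 counts unsuccessful uses: "Count QSECBAS = 'used, but not successfully' per patient display id full".
- Footnote 41 counts problems: "Count QSECBPRB = 'Yes, with Adverse Event' OR 'Yes, without Adverse Event' per patient display id full".

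SAP 16.1 carries all of this over to pre-hospital discharge and follow-up: "All analyses from chapter 15 Devices and Accessories - Implantation are repeated for these data".

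**The concern.** The use counts distinguish the cable under investigation from the cable already certified; the outcome counts do not. A reader of the tables sees how often PK-222-L was used, but not how many of those uses failed or gave a problem. The objective asks for evidence on the performance and usability of PK-222-L, and an unsuccessful-use count beside a use count is the plainest summary of that.

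The patient-cable table pools its models in the same way (footnote 50), but all of those are certified accessories. In the ECG-cable table, the pooling joins an investigational product to a certified one. Because use of PK-222-L is optional, the split between models is not fixed in advance, so the tables cannot be assumed to be almost entirely about one model.

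**Working it through.** The documents give no expected number of uses or failures by cable model, so there is no plan figure to reproduce. The check is whether the specified output fixes the PK-222-L failure count.

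**Step 1. Model condition in each row of SAP 15.1 (ECG cable).**

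| Row | Footnote | Condition on DIECBMDL |
|---|---|---|
| Any PK ECG cable used | 37 | both models named |
| PK-222-L used | 38 | PK-222-L |
| PK-222 EU used | 39 | PK-222 EU |
| Not successfully used | 40 | none |
| Any problem | 41 | none |

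**Step 2. Does another table cross model with outcome?** DIECBMDL, QSECBAS and QSECBPRB are each marked as not reported, which SAP 1.2 reserves for variables used only in derivations. No other specified table combines them.

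**Step 3. Does the case listing close the gap?** The ECG-cable listing covers every unsuccessful or problem use. It names the reason text and the programmer serial number. The row key contains helpvar model (SAP 5.9 and 15.1), so the model could be printed, but the SAP does not say that it is.

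**Step 4. What the summed counts imply.** Let nL and nEU be the summed footnote 38 and 39 counts, f the summed footnote 40 count, and x the PK-222-L failures. Then 0 ≤ x ≤ nL and 0 ≤ f − x ≤ nEU, which gives

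max(0, f − nEU) ≤ x ≤ min(f, nL).

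The splits below are assumptions: 50 uses, one ECG cable for each of the 50 implantations planned in Protocol 11.2.1.

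| nL / nEU (assumed) | f = 1: range of x | as share of nL | f = 2: range of x | as share of nL |
|---|---|---|---|---|
| 10 / 40 | 0–1 | 0–10% | 0–2 | 0–20% |
| 25 / 25 | 0–1 | 0–4% | 0–2 | 0–8% |
| 40 / 10 | 0–1 | 0–2.5% | 0–2 | 0–5% |

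The same bounds hold for footnote 41.

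**Step 5. Direct test.** Footnotes 37 to 41 were applied as written to four made-up logs, each with 30 PK-222-L uses, 20 PK-222 EU uses, one cable per patient and 3 failures. The PK-222-L failures were set to 0, 1, 2 and 3 in turn. All four gave identical tables, including the per-patient distributions: 47 patients with no unsuccessful use and 3 with one.

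**Step 6. When the tables do fix the count.** They do so if f = 0, if every use failed, or if one model was never used. They can also do so otherwise, because these rows are reported as distributions of counts per patient and not as sums. Suppose no patient has more than one cable of each model, f = 2, and one patient shows an unsuccessful-use count of 2. That patient had one failure of each model, so x = 1.

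**The case against.** The strongest reply is that little is lost.

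- **Adjudicated events.** The SAP 10.2 case listings, repeated for pre-hospital discharge and follow-up by SAP 11.1, give the related investigational device (DEIDV) and the cable ID for AEs and for DDs. They are not restricted to events that count for the endpoint; they also show those ruled out, with the reason. Protocol 18.3 defines a device deficiency broadly, including malfunctions and use errors, so many cable-caused failures should be reported as one.
- **Other problems.** SAP 13.1 separately tabulates hardware or software problems not mentioned elsewhere, including ECG recording. This is a partial further route, but it carries no cable model.
- **No rule broken.** Protocol 9.1 asks for use and evaluation to be documented in the CRFs, and they are: model, success and problem sit on the same accessory-log row. The study is exploratory, has no pass/fail criteria, and relies on discussing individual events.

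Most of this stands. A reader might infer that PK-222-L failures cannot be traced at all, or appear only in the pooled counts; the SAP 10.2 listings show otherwise. A reader might also infer that the split is never recoverable when both models are used and some uses fail; the per-patient distributions can sometimes fix it. Nor do the documents support a claim that Protocol 9.1 is breached.

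What remains is that the adjudicated listings hold events, not unsuccessful uses set against a number of uses. They do not supply the missing row, and they do not cover a use recorded as unsuccessful or problematic that led to no adjudicated AE or DD.

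**Conclusion.** The point holds as a reporting gap of minor weight. In the SAP 15.1 and 16.1 summary tables, unsuccessful uses and problems of PK-222-L are pooled with those of PK-222 EU, so the tables generally do not show its failures or problems out of its uses.

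The uses affected are those recorded as unsuccessful or problematic that generate no adjudicated AE or DD. They appear in the pooled counts and in a listing that may or may not print the model.

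The number of such uses cannot be stated in advance. With one or two failures in total, the summed counts leave the PK-222-L count open by one or two. The percentages above depend entirely on the assumed splits and are illustrations, not estimates for this trial. If no failure occurs or only one model is used, the ambiguity disappears, but that is not known when the SAP is written. The ADE/DD endpoints are not affected.

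**What to change.** Derive footnotes 40 and 41 twice, once with DIECBMDL equal to PK-222-L and once with DIECBMDL equal to PK-222 EU. Report each beside the matching use count from footnote 38 or 39, for implantation (SAP 15) and for pre-hospital discharge and follow-up (SAP 16). State in the ECG-cable case listing that DIECBMDL is printed. The ADE/DD derivations need no change.

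The cost is two more derived variables (four in place of two) and one listing column, all from data already collected, with no protocol change. Protocol 11.8 allows the SAP to be updated before database freeze or closure. The drawback is small per-model denominators, which is a reason to show counts beside uses and not percentages alone.

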## **15.2. Treatment of Missing and Spurious Data**

See general definitions in chapter 5.4.

## **15.3. Exclusion of Particular Information**

See general definitions in chapter 5.5.

No data are excluded from the specified analysis set and variables.

## **15.4. Descriptive Analyses**

For specification "Notes = descriptive", see general definitions in chapter 5.1.

## **15.5. Hypotheses & Statistical Tests**

There are no pre-defined statistical hypotheses.

## 16. Devices and Accessories – PHD & follow-up

### CIP chapter 7.5 Further data of interest

#### General information

- Implant type and model, all other implanted devices
- Lead model and programmer software version

*During implantation and follow-ups additional data on safety, performance and usability of the Renamic Neo system and accessories will be collected.*

*... Information on additionally used accessories or other implanted cardiac devices*

### 16.1. Analysis Set and Data Selection

All analyses are performed for patients in the PHD and follow-up analysis set using a specific data selection after implantation.

All analyses from chapter 15 Devices and Accessories - Implantation are repeated for these data. However, "implantation" will be replaced by and "PHD & follow-up".

---

 analysis set PHD FUP SAR = Yes  
Data selection for accessory log details with SVTYP ≠ implantation

## Abbreviations

ADE	Adverse Device Effect
AE	Adverse Event
AF	Atrial Fibrillation
CDMS	Clinical Data Management System
CI	Confidence Interval
CIP	Clinical Investigation Plan
CIR	Clinical Investigation Report
CRF	Case Report Form
DD	Device Deficiency
FU(P)	Follow-up
PHD	Pre-hospital discharge
SADE	Serious Adverse Device Event
SAE	Serious Adverse Event
SAP	Statistical Analysis Plan
SAR	Statistical Analysis Report
SOP	Standard Operating Procedure
SD	Standard Deviation
